3.3. Treatments of patients

Details concerning definitions on extent of exposure, treatment compliance and concomitant treatments are provided in Appendix 5.2 and provided in the Specifications document.

3.3.1. Global duration, extent of exposure and treatment compliance

Global duration (days), extent of exposure (treatment exposure (days) and treatment duration (days)) and treatment compliance (%) over the W000-W004 and the W000-W006 period will be described in the FAS and the SS.

Treatment compliance (over the W000-W004 and W000-W006 periods) will be also described in classes (< 80, [80; 120], and > 120%).

3.3.2. Concomitant treatments

All concomitant treatments taken at inclusion, during the treatment period (over the W000-W004 and W000-W006 periods) and after the last IMP intake will be described in the RS, by ATC code.

3.4. Efficacy analysis

General definitions are provided in Section 3.1.2. Details concerning efficacy criteria definitions are provided in Appendix 5.2.

3.4.1. Statistical hypotheses

The statistical hypothesis is based on a multi-contrast test.

The hypothesis of the test is:

$$H_0: c'\mu = 0 \text{ vs } H_1: c'\mu > 0.$$

Where:

- μ is a vector of mean response.
- c is a vector of contrast.

Due to the use of the MCPMod methodology, the overall Type I error rate across the assumed dose-response relationships will be controlled at a one-sided 2.5% level.

3.4.2. Primary efficacy criterion

Definition: The primary efficacy criterion is defined as relative reduction of Reference Ulcer area after 4 weeks of treatment on top of standard of care compared with baseline Reference Ulcer area assessed during study visits using a digital 3D imaging device.

3.4.2.1. Primary analysis

Primary analysis: the MCPMod method (Multiple Comparison Procedures and Modelling) will be applied to the primary efficacy endpoint in the FAS. The MCP-step corresponds to the establishing of a dose-response signal (the dose-response curve is not flat) and the Mod-step to the estimation of the dose-response curve.

The MCPMod method was introduced for developing robust dose-response evaluation strategies in Phase II trials (Bretz, Pinheiro and Branson, 2005). All details of this method are provided in Appendix 5.3.1.

More specifically, let Y_{ij} be the relative change from baseline at W004 for the patient j treated at the dose i of S42909.

We assume that:

$$Y_{ij} = \mu_i + \varepsilon_{ij}$$

$$\varepsilon_{ij} \stackrel{ind}{\sim} N(0, \sigma^2)$$

Where:

- $\mu_i = f(d_i, \theta)$ is the mean response at dose d_i for the dose response models $f(\cdot)$ parameterized by a vector of parameters θ .
- $i = 1, \dots, k$ where k is the number of doses.
- $j = 1, \dots, n_i$ where n_i the number of patients at the dose i .
- ε_{ij} is the error term for patient j within dose group i follows a normal distribution with mean 0 and variance σ^2 .

Dose-finding will be performed using the following set of predefined candidate models of $f(\cdot)$ defined by some couples (d^*, p^*) (dose per day, percentage of efficacy at this dose):

- Linear.
- Emax1 (200 mg, 90%).
- Emax2 (400 mg, 70%).
- Sigmoid Emax (200 mg, 10%) and (1000 mg, 90%).
- Logistic (200 mg, 10%) and (1000 mg, 90%).
- Exponential1 (400 mg, 10%).
- Exponential2 (800 mg, 10%).

See Appendix 5.3.1 for more details on each model.

The MCPMod procedure is based on a multi-contrast test. A unique dose-response contrast is associated with each dose-response model. This contrast is defined as the contrast that has the highest power, i.e., the highest probability of rejecting the associated null hypothesis of no effect, under this particular model. The computation of the optimal contrast is explained in Appendix 5.3.1.

The significance of the dose-response trend based on each model-specific contrast will be assessed using the following t statistics:

$$t_m = \frac{\sum_{i=1}^k c_{mi} \bar{Y}_i}{S \sqrt{\sum_{i=1}^k \frac{c_{mi}^2}{n_i}}}$$

Where :

- \bar{Y}_i is the empiric mean of the response within dose group d_i .
- m is the number of models.
- n_i is the number of patients within the dose group d_i .

- $S^2 = \sum_{i=1}^k \sum_{j=1}^{n_i} \frac{(Y_{ij} - \bar{Y}_i)^2}{N - k}$
- c_m is the vector of contrasts with $\sum_{i=1}^k c_{mi} = 0$

The dose-response tests identify the set of clinically relevant models. A multiplicity adjustment is taken into account in the MCP-step. The joint distribution of the m test statistics is taken into account to compute an adjusted critical value that defines the threshold for statistical significance.

Under the global null hypothesis of no treatment effect under any model, the test statistics follow a central multivariate t distribution with $N - k$ degrees of freedom and correlation matrix R . More details for matrix R are given in Appendix 5.3.1.

To derive the multiplicity-adjusted critical value, denoted by q , let $T_1; \dots; T_m$ denote the random variables that have the same joint distribution as $t_1; \dots; t_m$ under the global null hypothesis. The adjusted critical value q is found from :

$$\Pr(T_{max} > q) = \alpha$$

Where α is the pre-specified Family Wise Error Rate (FWER) level equal to 0.025 (one-sided test).

The set of clinically relevant dose-response model corresponds to the models associated with $t_i > q$. The adjusted p-value will be calculated according to the value of q .

Among the set of clinically relevant dose-response models, the best dose-response contrast will be identified as the contrast test with the maximum test statistics.

An estimation of parameters of the best model selected will be provided according to the observed data as well as a plot of this model.

If relevant, modelisation will be done even if no dose-response model is significant.

Multiplicity issues:

The multiplicity issue due to multiple dose-response models is corrected with the computation of an adjusted critical value and adjusted p-values.

Missing data handling: missing data will not be imputed.

Statistical elements:

Finally, the following elements will be provided in summary tables:

- Descriptive statistics and 95% CI of the primary criterion in each arm.
- The best dose-response selected.
- An estimation of parameters of the best model selected.

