3.1.2. General definitions

The following definitions will be considered:

- **IMP** is the treatment intake (S42909 or Placebo) post randomisation.
- **Analysable value** will be defined as any non-missing value.
- **Baseline value** will be defined as the last analysable value prior to the first IMP intake (*i.e.* before or the same date as the first IMP intake date).
Note: In case of patient included and/or randomised but not treated (*i.e.* patients with treatment duration equal to 0): value at baseline is defined as the last analysable value prior or equal to the date of the inclusion visit.
- **Post-baseline value** will be defined as any value recorded at a given timepoint after baseline.
- **Change from baseline** will be defined as the arithmetic difference between a post-baseline value and the baseline value for a given variable at a given time point.
- **Relative change from baseline** will be defined as : $100 * \text{change from baseline} / \text{baseline value}$.

For safety criteria (except for adverse events), the following definitions will be applied:

- A value is considered under treatment if the assessment date is between the first IMP intake date (excluded) over the W000 and W006 period and the last IMP intake date "+ 15 days" (included).

Note: for all definitions concerning value under treatment '+ 15 days' was calculated according to the half-life of the S42909.

- High emergent abnormal value under treatment according to the laboratory reference ranges is defined as value \leq ULN (Upper Limit of Normal laboratory reference range) or missing at baseline and $>$ ULN under treatment.
- Low emergent abnormal value under treatment according to the laboratory reference ranges is defined as value \geq LLN (Lower Limit of Normal laboratory reference range) or missing at baseline and $<$ LLN under treatment.

- High emergent abnormal value under treatment according to the cut-offs for PCSA (Potentially Clinically Significant Abnormal value) values is defined as value \leq ULS (Upper Limit used to define potentially clinically Significant abnormal values) or missing at baseline and $>$ ULS under treatment.
- Low emergent abnormal value under treatment according to the cut-offs for PCSA values is defined as value \geq LLS (Lower Limit used to define potentially clinically Significant abnormal values) or missing at baseline and $<$ LLS under treatment.

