3.4.2.3. Supplementary analyses

- To meet the secondary objective, the Minimal Effective Dose (MED) will be estimated using the selected model resulting from the primary analysis.

The MED is defined as:

$$MED = \min(d: f(d) > f(d_0) + \Delta, L(d) > f(d_0))$$

with Δ is the clinically relevant difference, $L(d)$ the lower confidence limit of the predicted mean value $f(d)$ at dose d.

The estimator will be provided considering a hypothesis of a clinically relevant effect as compared to placebo of 6.5%. A confidence interval will be provided by bootstrap method.

- The primary analysis will be repeated in the PPS.
- For RU area, description at each visit and the relative change from baseline to each visit will also be provided in FAS and PPS.
- Description of the relative change from W006 to W008 of the reference ulcer (RU) area, for patients with a non null value at W006, as well as the description of the relative change from W004 to W006, for patients with a non null value at W004, will be described in FAS and PPS.

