Linear	$E_0 = 32.5, \delta = 0.025$
Emax 1	$E_0 = 32.5, E_{max} = 30.6, ED_{50} = 22.2$
Emax 2	$E_0 = 32.5, E_{max} = 34.3, ED_{50} = 171.4$
Sigmoid Emax	$E_0 = 32.5, E_{max} = 32, ED_{50} = 447.2, h = 2.7$
Logistic	$E_0 = 31.3, E_{max} = 32.3, ED_{50} = 600, h = 182.1$
Exponential 1	$E_0 = 32.5, E_1 = 1.95, \delta = 428.9$
Exponential 2	$E_0 = 32.5, E_1 = 0.03, \delta = 174.4$

Optimal contrasts

The MCPMod procedure is based on a multi-contrast test. A unique dose-response contrast is associated with each dose-response model. This contrast is defined as the contrast that has the highest power, *i.e.*, the highest probability of rejecting the associated null hypothesis of no effect, under this particular model. The standardized version of the model is used and the predicted effects is computed under this standardized model:

$$u_{ij} = g_i(d_j, \theta_0)$$

Where:

- $j = 0, \dots, m$, with m the number of candidate model.
- i the dose.

The predicted effects can be computed using the initial values defined in the [Table \(5.3.1\) 1](#).

The optimal constraint is calculated from the predicted effects by centering and normalizing this vector.

The coefficients of the optimal constraint for each model are defined with the following formula:

$$c_{ij} = \frac{u_{ij} - \frac{1}{m+1} \sum_{l=0}^m u_{il}}{\sqrt{\sum_{l=0}^m (u_{ij} - \frac{1}{m+1} \sum_{l=0}^m u_{il})^2}}, j = 0, \dots, m$$

Where

- $j = 0, \dots, m$, with m the number of candidate model
- i the dose

Dose-response tests

The significance of the dose-response trend based on each model-specific contrast will be assessed using the following t statistics:

$$t_m = \frac{\sum_{i=1}^k c_{mi} \bar{Y}_i}{S \sqrt{\sum_{i=1}^k \frac{c_{mi}^2}{n_i}}}$$

where

- \bar{Y}_i is the empiric mean of the response within dose group d_i .
- m is the number of model.
- n_i is the number of patients within the dose group d_i .
- $S^2 = \sum_{i=1}^k \sum_{j=1}^{n_i} \frac{(Y_{ij} - \bar{Y}_i)^2}{N - k}$
- c_m is the vector of contrasts with $\sum_{i=1}^k c_{mi} = 0$

The dose-response tests identify the set of clinically relevant models. A multiplicity adjustment is taken into account in MCP. The joint distribution of the m test statistics is taken into account to compute an adjusted critical value that defines the threshold for statistical significance.

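### The one-sided primary test is set on a variable that, as the SAP defines it, goes negative when the ulcer heals

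*SAP*

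**What the plan says.** - **Criterion.** SAP 3.4.2 defines the primary criterion as "relative reduction of Reference Ulcer area after 4 weeks of treatment on top of standard of care compared with baseline Reference Ulcer area". This is positive when the ulcer shrinks.
- **Tested variable.** SAP 3.4.2.1, and again Appendix 5.3.1, let Y_ij "be the relative change from baseline at W004 for the patient".
- **Definition of that term.** SAP 3.4 tells the reader: "General definitions are provided in Section 3.1.2. Details concerning efficacy criteria definitions are provided in Appendix 5.2". In 3.1.2, relative change is 100 × change / baseline, and change "will be defined as the arithmetic difference between a post-baseline value and the baseline value". Appendix 5.2.3 covers linear advance, pain and diabetic status. It gives no formula for relative area reduction.
- **Direction of the test.** SAP 3.4.1 sets H1 as c'μ > 0 and says that "the overall Type I error rate across the assumed dose-response relationships will be controlled at a one-sided 2.5% level". In 3.4.2.1, "The set of clinically relevant dose-response model corresponds to the models associated with" a t statistic above the critical value q.
- **Curves.** In Table (5.3.1) 2 all seven candidate curves start at about +32.5 and rise.
- **MED.** SAP 3.4.2.3 takes the smallest dose with f(d) > f(d0) + Δ and a lower confidence limit above f(d0). On Δ it says: "The estimator will be provided considering a hypothesis of a clinically relevant effect as compared to placebo of 6.5"%.

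**The concern.** The test looks only in the upper tail, so the sign of Y_ij decides its result. A programmer who follows the cross-reference from 3.4 to 3.1.2 would compute a variable that becomes more negative as healing improves, then test whether it rises with dose. A real benefit would be missed, and a dose-related worsening of mirrored size would be declared a signal. The per-protocol repeat (3.4.2.3) and the repeat in centres where PK confirms intake (3.4.2.2) would inherit the error. The covariate-adjusted analysis in 5.3.2 refers only to the primary endpoint and has no sign conflict of its own.

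There is also a reporting question. SAP 3.4.2.1 asks for descriptive statistics of the primary criterion by arm, while 3.4.2.3 and 3.4.4 describe the same ulcer area as relative change from baseline. Read as written, W004 results would appear with opposite signs, and the SAP does not say how the two relate.

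**Working it through.** **1. Sign of the defined term.** With baseline area B and W004 area A, the natural reading of 3.1.2 gives 100 × (A − B)/B, and the criterion in 3.4.2 is 100 × (B − A)/B. One is the negative of the other. The phrase in 3.1.2 does not strictly fix the order of subtraction, but Appendix 5.2.3 writes the area difference for linear advance as visit minus baseline. At the mean responses assumed in SAP 1.3, the reduction scale runs from +32.5 (placebo) to +62.5 (maximum). The 3.1.2 scale runs from −32.5 to −62.5.

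**2. Reproducing the planned power.** Inputs from SAP 1.3, 3.4.1 and Table (5.3.1) 2: doses 0, 100, 200, 400, 800 and 1200 mg/day; SD 42; 27 per group; one-sided 2.5% over seven contrasts; curve parameters as printed.

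- Optimal contrast for equal arms: the model means, centred and scaled to unit length.
- Degrees of freedom: 6 × 27 − 6 = 156. Simulated critical value of the maximum t: q = 2.40.
- Non-centrality of each contrast: (√n / SD) × c'μ.

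Example, linear model. The means are 32.5, 35, 37.5, 42.5, 52.5 and 62.5, with average 43.75. The sum of squared deviations is 671.9, so c'μ = √671.9 = 25.92. Non-centrality is (√27 / 42) × 25.92 = 3.21, above q. With the sign reversed it is −3.21, far below q.

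Power from 1,000,000 simulated trials per model, and the dose at which each printed curve reaches placebo + 6.5 on the reduction scale:

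| True model | Power, reduction | Power, sign reversed | Dose at +6.5 (mg/day) |
|---|---|---|---|
| Linear | 84.9% | 0.001% | 260 |
| Emax 1 | 82.1% | 0.042% | 6 |
| Emax 2 | 81.6% | 0.003% | 40 |
| Sigmoid Emax | 92.4% | 0.0002% | 270 |
| Logistic | 90.7% | 0.001% | 387 |
| Exponential 1 | 84.5% | 0.011% | 629 |
| Exponential 2 | 82.6% | 0.040% | 939 |

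The plan's figures (at least 80% for every model, about 90% for the logistic) are reproduced on the reduction scale only. Exponential 2 is sensitive to the rounding of E1 to 0.03 in the SAP table: with unrounded parameters its power is 84.8% and its dose 934 mg/day. This does not affect the sign question.

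**3. The included sample.** The SAP reports 121 patients included, about 20 per group (121/6). If almost none are excluded, power is 68.3% to 82.3% on the reduction scale and at most 0.07% with the sign reversed.

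**4. MED.** Example on the reduction scale, linear: 6.5 / 0.025 = 260 mg/day. On the 3.1.2 scale all seven curves fall with dose, so f(d) − f(d0) is never above zero and no dose meets the rule.

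**5. Would it be noticed?** The pooled mean over six equal arms is +38 (exponential 2) to +56 (Emax 1) as a reduction, and −38 to −56 by 3.1.2. With a pooled SD of 43 to 44 and 121 patients, the standard error is 43/11 to 44/11, about 4. The sign is therefore visible without treatment codes.

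**The case against.** The strongest reply is that the documents already fix the scale. SAP 3.4.2.1 opens by applying MCPMod to the primary endpoint, which 3.4.2 has just defined as a reduction, and the Y_ij sentence only elaborates on it. SAP 1.3 labels +32.5% and +62.5% a relative change, and protocol 10.1.4 equates the area reduction with the relative change. The model stated for Y_ij has a mean of about +32.5 at dose zero, so a negative Y would contradict its own model. The order of subtraction in 3.1.2 is a reading and not an explicit formula. The collapse in power only says that a one-sided test fails when its sign is flipped. The required summaries by arm, or the blind review in protocol 14.2, could expose the error. The table templates are in a separate document that was not seen.

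Most of this stands: the intent is recoverable, and literal coding is not the likely outcome. It does not remove the conflict. The variable in the test is given by a defined term whose natural reading has the wrong sign, and no sentence states a sign convention for Y_ij. Corrected before unblinding, the sign is a clarification. Corrected afterwards, it could look like a data-driven change. The point about the descriptive tables is limited to what the SAP text says, because the templates may settle it.

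**Conclusion.** The concern holds as a specification error in two sentences of the SAP. It is not a design flaw. Followed literally, the plan would take the primary test from 81.6%–92.4% power to about 0.04% or less and leave no MED to estimate. These figures rest on the SAP's own assumptions (30-point maximal effect, SD 42, 27 evaluable per group, the seven printed curves) and on reading change as post-baseline minus baseline. On the intended scale the sample-size calculation is sound and the error rate is unaffected. The sentences should be corrected before unblinding because the primary test is one-sided.

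**What to change.** In SAP 3.4.2.1 and 5.3.1, define Y_ij = 100 × (baseline area − W004 area) / baseline area, positive when the ulcer shrinks. Add one sentence stating that:

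- this relative reduction is the negative of the relative change in 3.1.2;
- it is the scale for every MCPMod analysis and for the MED;
- the descriptive ulcer-area tables in 3.4.2.3 and 3.4.4 use a named sign.

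The cost is two or three lines of text. Data, candidate models, alpha and sample size do not change. The programs and table templates were not available. If any program already applies the 3.1.2 formula to Y_ij, one sign has to be changed there.

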3.4.2.2. Sensitivity analyses

- The MCPMod method adjusted on diabetes status factor and prognosis criteria on size and age of the ulcer factor will be applied to the primary efficacy endpoint in the FAS. Details of the MCPMod approach with covariate-adjusted inferences are provided in Appendix 5.3.2.
- The primary analysis will be repeated in the FAS with patients from centers where PK results confirm the treatment intake.

